VIE SCOPE VERSUS MACINTOSH LARYNGOSCOPE IN EXPECTED EASY AIRWAYS: A RANDOMIZED CONTROLLED TRIAL

NCT NUMBER:
NCT06149338

21/08/2024

STUDY PROTOCOL

Ethics

The study protocol was approved by the Scientific Committee (approval number: 141/09.07.2023). Since the strategies employed in both study groups are considered components of standard care, and the study involved patients undergoing elective and nonelective surgery or being treated in the emergency settings, the committee waived the necessity for written informed consent. The study was registered on ClinicalTrials.gov (NCT06149338) on 04.01.2024 and was in accordance with the principles of the Declaration of Helsinki and Good Clinical Practice guidelines.

Study design

A prospective, randomized, single-blind, superiority, clinical trial has been conducted since 26.01.2024. The intubations were performed by the same resident of anesthesiology, who had already completed successfully at least 50 intubation attempts with each one of the two examined laryngoscopes, before the beginning of the patient enrollment into the study, in order to eliminate any impact from a different learning curve of any laryngoscope and to gain competency, although concurrently there are limited data for Vie Scope, fostering its short learning curve, despite the mentioned necessity of previous practice with straight blade devices. Every intervention was made under the supervision of an experienced Anesthesiologist consultant. In case of certified or possible COVID-19 infection of the patient, the airway operator was instructed to use the required PPE.

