The current study included patients of both sexes. Apart from the gender, the age (\geq 18 years old) and the Body Mass Index (B.M.I.: 18.5 – 30 kg/m²) were considered as inclusion criteria of this study. A positive or negative rapid test for COVID-19 or possible contamination of the patient was documented as well, without affecting the patient's eligibility for the study inclusion. Also, every patient underwent an adequate airway assessment, including airway history and physical examination, preoperatively or in the emergency settings, when feasible, to distinguish the patients with anticipated easy airways management. The chin protrusion (upper lip bite test), the thyromental distance and the Mallampati score were mostly evaluated, due to their efficacy in detecting an anticipated difficult airway. Consequently, the higher a patient could bite the upper lip with the lower incisors, the thyromental distance > 3 ordinary fingerbreadths and the Mallampati scores 1, 2 were positive predictive factors of an expected easy airway. Despite the high sensitivity of the upper lip bite test, the low sensitivities of other tests, such as the Mallampati score, and the confined airway assessment in emergency settings or patient cooperation necessitated the adoption of the Cormack - Lehane classification as a recruitment criterion of this study. According to this scale, the glottis visualization grades 1, 2a, 2b, after direct laryngoscopy, were compatible with easy endotracheal intubation, making these patients eligible participants in the present study. In contrast, patients with age under 18 years old, with BMI under 18.5 kg/m² and over 30 kg/m², inability to bring mandibular incisors anterior to maxillary incisors, thyromental distance < 3 ordinary

fingerbreadths, Mallampati scores 3, 4 and Cormack - Lehane classification grades 3 and 4 were excluded from this clinical trial.

The randomization of the patients was generated immediately before the anesthesia induction, after the investigator Anesthesiologist trainee was assigned to the patient, either in the operating room or in the emergency settings, using sealed opaque envelopes, that contained demographic data and medical background of the participants in pseudonymized form. The allocation ratio was 1:1 to either Vie Scope or Macintosh laryngoscope. The patients remained blinded to the intervention procedure, while this was not feasible for the airway operator, due to the study's nature.

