After the tube's cuff was inflated, until there was no air leak from the trachea, the correct ETT's placement was verified in both groups by the patient's ventilation. The choice of the size and the type of the ETT was at the discretion of the airway operator. In addition, the laryngeal view was estimated, under direct laryngoscopy with each laryngoscope, according to the Cormack - Lehane grading system. The airway operator was prompted to perform any external laryngeal manipulation, such as the backward, upward, rightward pressure (BURP), or to use any assistant equipment, like bougies, stylets, forceps, lubricant gel or spray, for optimizing the laryngeal view and facilitating the intubation process. The supervisor consultant would be involved in case of two failed intubation attempts by the trainee, or whenever the situation required the intervention of an experienced Anesthesiologist.

Outcome measures

The primary outcome measures were the first attempt intubation success rate and the required mean intubation time. The intubation time was defined as the time interval from the insertion of the laryngoscope into the patient's mouth, until the inflation of the ETT's cuff of each patient.

Contrarywise, the overall intubation success rate and the glottis visualization, based on the Cormack - Lehane classification, were regarded as the secondary outcomes.

STATISTICAL ANALYSIS

The statistical analysis was performed with SAS version 9.4 (SAS Institute, Cary, NC, USA) along with Microsoft Excel 2007 for data collection. For the descriptive statistics, quantitative variables were presented as means and standard deviations (SD) as well as using medians and quartiles 1 and 3 (Q1 and Q3 respectively). Qualitative variables were presented using the relative frequencies and the relevant percentages. For the inferential part of the analysis, the Kruskal – Wallis test was applied for the analysis of numerical data, because they did not follow a normal distribution, according to the Kolmogorov - Smirnov test, while the χ^2 test and, if required, the Fisher's exact test were performed for the categorical data. All tests were two-sided, the confidence intervals (CIs) were determined as 0.95 and thus significance cut-off level was for $p < 0.05$.

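### Both primary outcomes are compared with unstratified tests although setting is known at randomisation: a modest, avoidable loss of precision, mainly for intubation time

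*Combined protocol and SAP*

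**What the plan says.** **Outcomes.** The Outcome measures section states: "The primary outcome measures were the first attempt intubation success rate and the required mean intubation time".

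**Tests.** Under STATISTICAL ANALYSIS, the Kruskal-Wallis "test was applied for the analysis of numerical data, because they did not follow a normal distribution". For proportions the chi-square test and, "if required, the Fisher's exact test were performed for the categorical data". The section adds: "All tests were two-sided, the confidence intervals (CIs) were determined as 0.95". It names no covariate, regression model or stratified test.

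**Randomisation (Study design).** Allocation is 1:1 by sealed envelope just before induction, "either in the operating room or in the emergency settings". No stratification factor is named.

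**Baseline information (Study design).** Age and BMI are eligibility items. On infection status: "A positive or negative rapid test for COVID-19 or possible contamination of the patient was documented as well". On the airway: "The chin protrusion (upper lip bite test), the thyromental distance and the Mallampati score were mostly evaluated", but the same section concedes that assessment in emergencies was limited and made only where feasible. For confirmed or possible infection, "the airway operator was instructed to use the required PPE"; nothing says that PPE use was recorded.

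**The concern.** The Ethics section describes elective surgery, nonelective surgery and emergency patients. Eligibility narrows BMI, Mallampati class and thyromental distance, and one resident performs every intubation. Setting and infection status are not narrowed in this way, so they are the likeliest remaining sources of variation in intubation time. Neither the randomisation nor the analysis takes account of them.

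Two things are at stake. Variation that setting could explain stays in the error term, so the comparison of times is less precise than it could be. And if emergency cases fall unevenly between the arms, the observed device difference carries part of the difference between settings, with nothing in the analysis to separate them.

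**Working it through.** **Inputs from the documents.** Two-sided 5% level with 95% intervals (the two agree: 1 − 0.95 = 0.05); 1:1 allocation; one binary and one continuous primary outcome. There is no sample size, SD, success rate or power figure to reproduce. Every N, R², prevalence and effect below is therefore an assumption.

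**1. Gain for intubation time.** If baseline data explain a share R² of the variance of log time, the interval width is multiplied by √(1 − R²). A comparison with 80% power moves to Φ(2.8016/√(1 − R²) − 1.96), where 2.8016 = 1.96 + 0.8416.

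| Assumed R² | CI narrower by | Power |
|---|---|---|
| 0.02 | 1% | 81% |
| 0.05 | 2.5% | 82% |
| 0.10 | 5% | 84% |
| 0.20 | 11% | 88% |
| 0.30 | 16% | 92% |

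**2. Gain for first-attempt success.** Let a factor with 30% prevalence have success rates q and q₂ in its two levels, and let overall success be p. Its explained share is 0.3 × 0.7 × (q − q₂)²/[p(1 − p)]. For p from 85% to 95% and odds ratios from 2 to 5 this runs from 0.0058 to 0.0847. The interval narrows by 1 − √(1 − 0.0058) = 0.3% up to 1 − √(1 − 0.0847) = 4%.

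**3. Chance imbalance.** These are exact binomial probabilities that two equal arms differ by 10 percentage points or more:

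| Prevalence | N = 60 | N = 100 | N = 200 |
|---|---|---|---|
| 30% | 48% | 33% | 14% |
| 10% | 28% | 13% | 2.5% |

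If emergency cases take 0.3 longer on the log scale, a 10-point imbalance moves the device difference by 0.10 × 0.3 = 0.03, a factor of e^0.03 = 1.03. An assumed device effect of 0.2 is a factor of e^0.2 = 1.22.

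**4. Validity of the planned test.** Across simulations with N from 60 to 200 and R² from 0.05 to 0.30, the unadjusted Kruskal-Wallis test rejected a true null in 4.1% to 5.3% of trials. A further run gave 3.9% to 5.6%.

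**5. Which adjusted analysis.** Assume log-time error SD 0.35, a setting shift of 0.3 (30% prevalence), a second binary factor with shift 0.2 (50%), and a device effect of 0.2.
- Total R² = (0.21 × 0.09 + 0.25 × 0.04)/(0.0189 + 0.0100 + 0.1225) = 0.0289/0.1514 = 0.19. Setting alone gives 0.0189/0.1514 = 0.125.
- Normal errors, log-time model with the full covariate list and robust standard errors: power 79% against 70% for the rank test at N = 100, and 55% against 48% at N = 60. An unadjusted t-test on log time already reaches 73% and 50%, so part of the gain comes from leaving ranks.
- No prognostic covariate: 79% for both at N = 100; 54% against 55% at N = 60.
- 10% of intubations prolonged (an added exponential term with mean 1 on the log scale): the adjusted model drops to 46% against 59% for the rank test at N = 100, and 31% against 40% at N = 60. A separate run at N = 100 gave 48% and 62%, and a rank test stratified by setting gave 66%. The stratified rank test lost almost nothing when setting was not prognostic.

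**The case against.** The strongest defence is that randomisation makes the unadjusted comparisons valid, that one operator and narrow eligibility leave a fairly uniform sample, and that no figure in the documents shows any covariate to be prognostic. The first part stands in full. The second holds for BMI and airway scores but not for setting or infection status. The third limits what can be said about size; it does not argue against stratifying, because a weak stratifier costs very little.

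A reader might infer several stronger points that the documents do not support:
- **That chance imbalance makes the planned tests wrong.** Their error rate already allows for it, and the simulations hold near 5%.
- **That all useful covariates were recorded before randomisation.** Airway scores were limited in emergencies, PPE is an instruction only, and the time at which COVID-19 status was documented is not given. Treating COVID-19 status as a measure of PPE use is also an inference.
- **That both outcomes lose much precision.** For first-attempt success the loss is slight.
- **That a covariate-adjusted log-time model should become the primary test at no cost.** The time runs until cuff inflation, and the plan foresees failed attempts and consultant involvement, so some long times are plausible. In that case the model loses power, and robust standard errors do not restore it. It also estimates a ratio of geometric means, which is not a difference in mean times.

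There is also a timing objection. Enrolment began on 26.01.2024, and the statistical section is in the past tense and already reports non-normality. The documents do not say whether outcomes have been seen by arm. If they have, a new primary analysis would be post hoc.

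**Conclusion.** The point holds as a matter of efficiency and interpretation, not as an error. Both primary outcomes are planned without adjustment and without described stratification, although setting is known at randomisation, age and BMI are eligibility items, and COVID-19 status is documented. For intubation time the plausible gain runs from about 1 power point (R² 0.02) to 8 (R² 0.20), or 12 if R² reached 0.30. In the scenario with prolonged intubations, stratifying the rank test by setting added 4 points (66% against 62%). For first-attempt success the gain is marginal. All of these sizes rest on assumed N, R², prevalences and effects. The imbalance argument carries most weight if the trial is small and emergency cases are common; neither is stated.

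**What to change.** - **Intubation time:** use a van Elteren test stratified by setting (operating room or emergency), the stratified form of the planned rank test.
- **First-attempt success:** use a Cochran-Mantel-Haenszel test and a Mantel-Haenszel risk difference with 95% CI, stratified by setting.
- **Definition:** define setting by place of randomisation, and state where nonelective surgery falls.
- **Sensitivity:** keep the unstratified Kruskal-Wallis and chi-square or Fisher tests.
- **Supportive estimate:** fit a linear model for log time with device, setting, COVID-19 status, BMI and age, with robust standard errors. Report the adjusted ratio of geometric means with 95% CI.
- **Covariates to leave out:** PPE use and Mallampati class, unless recorded for every patient before randomisation; and Cormack-Lehane grade in any case, since it is observed after randomisation with the allocated device and is a secondary outcome.
- **Timing:** if outcomes have already been examined by arm, label every adjusted analysis as supportive and leave the planned tests as primary.

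The cost is SAP wording and a few extra analyses of data that should already be in hand, with a small loss of efficiency if setting turns out not to be prognostic.
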